Our goal is to create an AI-assisted diagnostic tool that can be easily integrated into clinical workflows, offering a cost-effective and accessible solution for osteoporosis screening.

• **Objectives:** The primary objective is to curate a comprehensive dataset of X-ray images sourced from publicly available domains and local health facilities, encompassing a diverse representation of patient demographics, geographic locations, and equipment variations. Building upon this dataset, we seek to develop a robust artificial intelligence model capable of prediction of bone mineral density from X-ray images.

The specific objectives of the study are:

- a) To develop a deep learning convolutional neural network (CNN) model that can accurately predict Bone Mineral Density (BMD) values from Xray images, using both prospective and retrospective data collection methods.
- b) To validate the AI model's performance on a diverse dataset encompassing a broad demographic, including variables such as age, gender, height, weight, menopausal status, and the presence of comorbidities like cardiovascular disease and diabetes.
- c) To evaluate the model's performance using a range of metrics, including Area Under the Precision-Recall Curve (AUPRC), accuracy, Mean Absolute Error (MAE), and Pearson Correlation Coefficient (PCC), ensuring its robustness in predicting BMD.
- d) To assess the usability and interpretability of the AI model's output by healthcare professionals, determining its integration into clinical practice and its impact on the diagnostic workflow efficiency.
- e) To measure the generalizability and adaptability of the model across various healthcare settings, ensuring the AI system's reliability on X-ray images from different populations and regions.

- f) To investigate the model's potential in enhancing early detection and treatment planning for osteoporosis by providing a non-invasive, cost-effective tool for BMD estimation, potentially leading to better patient management and outcomes.
- g) To assess the AI model's role as a decision support tool in determining the necessity for additional diagnostic procedures, such as DEXA scans, thereby optimizing patient care pathways and potentially reducing healthcare costs.

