- d) **Methods of Data Collection:** The following fields will be recorded in the data collection for this study:
 - Patient ID (unique identification number)
 - Date & time of the data input
 - Age
 - Gender
 - Phone number
 - X-ray image (hip or spine)

- DEXA scan result
- BMI
- Menopausal status
- Diabetes
- Cardiovascular disease and other clinical covariates

The X-ray images, and DEXA scan result of the subjects along with the relevant clinical covariates will be used to design the algorithms. The standard test status and the corresponding result will be used as the ground truth for our detection algorithm.

e) **Data Interpretation:** Upon the conclusion of data collection, exploratory data analysis to assess the distribution of patients across different demographics and clinical factors, including age, gender, menopausal status, presence of cardiovascular diseases, diabetes, and their correlation with BMD values. This process will ensure a comprehensive understanding of the dataset's characteristics and the establishment of a balanced dataset that represents a wide spectrum of patient profiles.

The refined dataset will serve as the foundation for training and evaluating our AI model, specifically designed for the regressionbased prediction of BMD from X-ray images. Our AI algorithm will leverage CNN to process X-ray images and predict BMD values, aiming to identify potential cases of osteopenia, osteoporosis, and normal.

To ascertain the model's performance and its clinical applicability, we will compare the AI-generated predictions with actual BMD measurements obtained from DEXA scans. This validation process will involve collaboration with orthopedic specialists and radiologists who will review the AI predictions in the context of their clinical experience and available patient information.

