f) Statistical Analysis: Upon finalizing the dataset, our statistical analysis will concentrate on evaluating the artificial intelligence model's capability to predict BMD from X-ray images accurately. Performance metrics such as Mean Absolute Error (MAE), Pearson Correlation Coefficient (PCC), Area Under the Precision-Recall Curve (AUPRC), and accuracy will be employed to meticulously assess the model's performance. To ensure the reliability of our findings, we will implement k-fold cross-validation techniques, providing a framework for evaluating our model across various subsets of data. This approach will allow us to calculate mean values and standard deviations for each performance metric, offering a comprehensive understanding of the model's predictive accuracy and consistency. The culmination of our analysis will involve a comparative review of different CNN architectures and training methodologies to determine the most effective strategy for BMD prediction from X-ray images.

Utilization of Results: The study results will play a crucial role in the development and evaluation of an automatic BMD prediction algorithm for osteoporosis screening. The algorithm's primary objectives are:

a) BMD Prediction: To accurately predict BMD values from X-ray images, facilitating an automated assessment tool for early detection of osteoporosis and osteopenia. This tool aims to bridge the gap in accessibility to BMD testing, especially in resource-limited settings.

b) Clinical Decision Support: To aid healthcare professionals by providing automated BMD assessments, enhancing their ability to make informed decisions regarding patient care. The model's predictions can help prioritize patients who need further testing or intervention, streamlining the diagnostic process.

c) Correlation Analysis: To explore and identify significant relationships between BMD or osteoporosis and collected clinical covariates such as age, gender, menopausal status, cardiovascular diseases, and diabetes. This analysis aims to enhance understanding of the factors influencing bone health, contributing to personalized and more precise osteoporosis risk assessment and management strategies.

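### The choice of the best CNN strategy has no deciding metric, and the SD over folds, the only stated measure of uncertainty, cannot show whether one architecture beats another (minor)

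*Protocol*

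**What the plan says.** Methodology f) names four measures. The list opens with MAE and PCC and goes on: "Area Under the Precision-Recall Curve (AUPRC), and accuracy will be employed to meticulously assess the model's performance". None is called primary or deciding. Specific objective c) gives the same four, again unranked: "To evaluate the model's performance using a range of metrics".

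For reliability, section f) states: "we will implement k-fold cross-validation techniques, providing a framework for evaluating our model across various subsets of data". The number of folds is not given. The stated use of the folds is to "calculate mean values and standard deviations for each performance metric", which the protocol presents as a full account of accuracy and consistency.

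The section closes with the choice itself: "a comparative review of different CNN architectures and training methodologies to determine the most effective strategy for BMD prediction". It gives no rule for the case where the metrics disagree and no interval for a difference between strategies.

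Methodology e) Data Interpretation describes one common dataset: "The refined dataset will serve as the foundation for training and evaluating our AI model". It also describes the model as a regression on BMD, whose predictions then serve to identify osteoporosis, osteopenia and normal cases.

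**The concern.** The protocol commits to naming a best strategy and calls this the end point of its analysis. Two things it fixes do not serve that purpose.

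First, the four metrics measure different things. PCC ignores a constant offset in predicted BMD, and MAE does not. AUPRC depends only on ranking, while accuracy depends on a cut-off. With no order among them, the reported winner can follow whichever metric looks favourable.

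Second, the fold SD describes how one model's score moves from fold to fold. The question is whether model A beats model B on the same patients, and that needs the variability of the difference. Writing Var(A − B) = Var(A) + Var(B) − 2 Cov(A, B), separate summaries for each model say nothing about the covariance. Much of the scatter is patient mix that both models share. Without an interval for the difference, a best architecture can be announced among models that are equally good.

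**Working it through.** **1. The plan's own figure.** Methodology b) gives Z = 1.96, precision 0.05, prevalence 0.373, sensitivity 0.911 and specificity 0.689.
- N_sen = 1.96² × 0.911 × 0.089 / (0.05² × 0.373) = 334.01, so 335.
- N_spec = 1.96² × 0.689 × 0.311 / (0.05² × 0.627) = 525.13, so 526.

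Both reproduce, and the target is 600. The calculation concerns the precision of one algorithm. It is not wrong on this point, and it does not address a comparison of architectures.

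**2. Implied accuracy.** 0.373 × 0.911 + 0.627 × 0.689 = 0.3398 + 0.4320 = 0.772. This takes accuracy as binary (osteoporosis or not).

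**3. What a fold SD measures.** From patient sampling alone, the expected SD of accuracy over folds is √(0.772 × 0.228 / fold size).
- k = 5 (120 per fold): √(0.1760/120) = 0.038.
- k = 10 (60 per fold): √(0.1760/60) = 0.054.

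The same model on the same 600 patients has a different SD because k changed. It is not the standard error of the model's score, nor of a difference between models.

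**4. Standard error of a difference in accuracy, N = 600, two models of equal accuracy.**
- Treated as independent: √(2 × 0.772 × 0.228 / 600) = 0.0242.
- Paired: √(d/600), where d is the share of patients that only one model classifies correctly. The protocol gives no d, so it is assumed.

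| d | Paired SE | Variance ratio, independent to paired |
|---|---|---|
| 10% | 0.0129 | 3.52 |
| 15% | 0.0158 | 2.35 |
| 20% | 0.0183 | 1.76 |

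The half-width of a 95% interval is 1.96 × 0.0242 = 0.047 unpaired and 0.025 to 0.036 paired. The gain vanishes if the models' errors are unrelated, since d is then 2 × 0.772 × 0.228 = 35%.

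**5. Does pairing change the winner?** On MAE it does not. The mean of the per-patient differences equals the difference of the means. In simulations with N = 600, a true MAE 7% lower and error correlation from 0 to 0.9, the lower mean MAE picked the better model in 95% to 100% of runs. In the same runs the mean ± SD ranges over folds overlapped in 85% to 90% (k = 5) and about 99% (k = 10). The means pick well, but the fold SDs do not show whether the difference is real.

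**6. Do the metrics agree?**
- Example: true BMD SD 0.15. Model A has error SD 0.08 and no offset. Model B has error SD 0.075 and a constant offset of 0.05. B wins on PCC (0.895 v 0.883). A wins on MAE (0.064 v 0.073) and slightly on accuracy (0.852 v 0.847).
- Equally good architectures (N = 600, error correlation 0.7): the four metrics did not all name the same winner in about 62% of runs with two architectures, 83% with four and 88% with six.
- One architecture truly 7% better on MAE (error correlation 0.7 to 0.9): accuracy failed to pick it in 13% to 21% of runs, AUPRC in 4% to 15%, and MAE in 0% to 2%.

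Effect sizes, correlations and k in steps 5 and 6 are assumptions, because the protocol gives none.

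**The case against.** A reader might infer that the best CNN is to be chosen by setting fold means and SDs side by side, so that real differences are missed and the plan has far less power than the data allow. The document does not support this. The sentence on fold means and SDs and the sentence on the comparative review stand next to each other, but neither says that the first decides the second. No unpaired test and no overlap rule is written, and a paired contrast is not excluded. An analysis plan that is not shown may supply one. Differences would be missed only if overlapping bars or an unpaired test were read as no difference. Step 5 shows that simply taking the lower mean MAE picks well. This objection stands in full.

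Three further points have weight.
- Disagreement among equally good models does not lead to a worse choice. That is true. The harm there is an unsupported claim of a winner. Where one model is truly better, step 6 shows that the metric does matter.
- The regression aim in Methodology e) points towards the continuous metrics. It does, but it does not separate MAE from PCC, and the example in step 6 turns on exactly that.
- Methodology e) speaks of three groups, so an accuracy of 0.772 on a binary class may not be the accuracy that is reported. The standard errors in step 4 are therefore illustrative.

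Finally, this is a minimal-risk model-development project, and the protocol ties no participant's treatment to which CNN wins. That limits the severity.

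**Conclusion.** The point holds in a limited form. The protocol commits to naming the most effective strategy, lists four metrics without order, and offers the fold SD as its only measure of uncertainty. The winner can depend on the metric read, and a fold SD cannot show that one architecture is better than another on the same patients.

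Pairing gives a valid and narrower interval for the difference: a standard error of 0.013 to 0.018 against 0.024 for accuracy. This rests on N = 600, the protocol's assumed sensitivity, specificity and prevalence, and an assumed 10% to 20% of discordant patients. It is not shown that the plan misses real differences or lacks power, and the stated sample size is unaffected. Severity: minor.

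**What to change.** In Methodology f):
- Run every architecture and training method on the same fixed folds.
- Before the first comparison, name MAE of BMD as the deciding metric, in line with the regression aim in Methodology e). Call PCC, AUPRC and accuracy descriptive.
- For each comparison, report the paired per-patient difference in absolute error with a 95% bootstrap interval over patients. Claim superiority only if the interval excludes zero.

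This takes two or three sentences. It uses predictions that the study will produce anyway and needs no extra patients. The small downside is that fewer claims of a best architecture will be possible.

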- **Rationale:** The early detection and treatment of osteoporosis are crucial in preventing fractures and ensuring the quality of life for individuals at risk. However, in developing countries like Bangladesh, the standard method for assessing bone health, DEXA, is not widely accessible due to its cost and the scarcity of specialized equipment and trained personnel. Consequently, many cases of osteoporosis remain undiagnosed until a fracture occurs, which significantly impacts patient outcomes and healthcare costs.

The current pathway for osteoporosis suspicion in Bangladesh typically begins with an X-ray prompted by symptoms of pain or fracture. If osteoporosis is suspected, a subsequent BMD test is recommended. This twostep process not only increases the financial burden on patients but also delays the diagnosis and treatment of osteoporosis, especially in rural areas where BMD testing facilities are scarce.

Addressing these challenges, our research proposes the use of deep learning algorithms to predict BMD values directly from X-ray images, which are more readily available and cost-effective than DEXA scans. By training a CNN with a dataset that includes demographic and clinical covariates, such as age, gender, menopausal status, cardiovascular disease, and diabetes, our AI model aims to identify correlations that can accurately predict BMD [15]. In this way, the developed AI model is intended to function as an assistive tool, providing a preliminary assessment to guide physicians on whether a more expensive and resource-intensive DEXA scan is warranted. This approach could substantially streamline the diagnostic process, making it more efficient and potentially reducing unnecessary medical expenses for patients.

- **Methodology:** In our data-driven approach to developing a predictive model for Bone Mineral Density (BMD) from X-ray images, we will collect and utilize a comprehensive dataset that includes X-ray images and BMD reports alongside demographic and clinical details of the subjects. The methodology will ensure patient privacy and data security, with all personally identifiable information being excluded from the dataset.

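### The only model comparison named is CNN against CNN, so the planned analysis would not show what the X-ray contributes beyond age, sex, BMI and similar items

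*Protocol*

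**What the plan says.** The Protocol speaks about covariates in two ways.

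- **Rationale:** "By training a CNN with a dataset that includes demographic and clinical covariates, such as age, gender, menopausal status, cardiovascular disease, and diabetes", the model is meant to predict BMD. Methodology d) Methods of Data Collection says that images and DEXA results "along with the relevant clinical covariates will be used to design the algorithms". The recorded fields there include age, gender, BMI, menopausal status, diabetes and cardiovascular disease.
- **Methodology e) Data Interpretation** describes a CNN that processes X-ray images. Methodology f) Statistical Analysis gives the aim as "evaluating the artificial intelligence model's capability to predict BMD from X-ray images accurately".

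Section f) lists "Performance metrics such as Mean Absolute Error (MAE), Pearson Correlation Coefficient (PCC), Area Under the Precision-Recall Curve (AUPRC), and accuracy", summarised by k-fold cross-validation. It ends with a "comparative review of different CNN architectures and training methodologies", which is the only comparison between models that it names.

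Two other planned analyses come near the question. Section e) says "we will compare the AI-generated predictions with actual BMD measurements obtained from DEXA scans", but DEXA there is the ground truth and not a competing predictor. Utilization of Results, item c), plans "To explore and identify significant relationships between BMD or osteoporosis and collected clinical covariates", which concerns association and gives no predictive benchmark.

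Objective g) and the Rationale propose the tool as a guide to who needs a DEXA scan.

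**The concern.** The conclusion is worded for the image, but the metrics describe whatever model is fitted. If that model also takes in covariates, its MAE, PCC and AUPRC mix two sources of information, and comparing one CNN with another does not separate them.

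The Protocol's own Introduction shows that this could matter. It reports osteoporosis risk of 43.2% in women and 30.3% in men, against 37.3% overall, rising with age. It also reports 78% in cardiovascular patients and 90% in people with multimorbidity. By this account, some items on the study's own questionnaire already separate patients.

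The intended use is at stake. A tool that decides who goes on to DEXA, justified by cost and access, invites the question of whether a few questionnaire items would do nearly as well. The analysis as written would not answer it.

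**Working it through.** **Step 1. The plan's own figures.** The sample size in Methodology b) uses z = 1.96, precision 0.05, prevalence 0.373, sensitivity 0.911 and specificity 0.689.

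- Sensitivity: 1.96² × 0.911 × 0.089 / (0.05² × 0.373) = 334.02, rounded up to 335.
- Specificity: 1.96² × 0.689 × 0.311 / (0.05² × 0.627) = 525.15, rounded up to 526.

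Both reproduce. They contain no term for a comparison between models, so they neither support nor weaken this point.

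**Step 2. Gain in MAE from the image.** The Protocol gives no covariate-only accuracy, so all PCC values here are assumptions. For calibrated predictions with normal errors, MAE is proportional to √(1 − r²). With covariate-only PCC r₀ and full-model PCC r₁, the relative gain is 1 − √(1 − r₁²) / √(1 − r₀²).

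The roots are 0.9165 for r = 0.4, 0.8660 for 0.5, 0.8000 for 0.6 and 0.7141 for 0.7. For 0.5 to 0.6, the gain is 1 − 0.8000/0.8660 = 7.6%.

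| Covariate-only PCC | Full model 0.6 | Full model 0.7 |
|---|---|---|
| 0.4 | 12.7% | 22.1% |
| 0.5 | 7.6% | 17.5% |
| 0.6 | 0% | 10.7% |

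Against a prediction that uses only the mean (r₀ = 0), a full-model PCC of 0.6 gives 1 − 0.8000 = 20%. A model can thus look 20% better than no information when the image accounts for 7.6%, or for nothing.

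**Step 3. The same point from a single reported result.** Suppose the final PCC is 0.70. The image's partial correlation given the covariates is √((0.49 − r₀²) / (1 − r₀²)).

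- r₀ = 0.3: √(0.40/0.91) = 0.66
- r₀ = 0.5: √(0.24/0.75) = 0.57
- r₀ = 0.6: √(0.13/0.64) = 0.45
- r₀ = 0.7: 0

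The same reported figure fits a large image contribution or none, depending on a quantity that the plan does not estimate.

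**Step 4. Is the planned number of patients enough for the added comparison?** With four covariates, two-sided 5% and the Fisher z approximation, power is Φ(atanh(ρ) × √(N − 3 − 4) − 1.96).

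| Partial correlation ρ | N = 600 | N = 526 |
|---|---|---|
| 0.12 | 84% | 78% |
| 0.15 | 96% | 93% |

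This treats the image score as fixed and assumes complete covariates in every patient, so it is on the favourable side.

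**The case against.** **The model may be image-only.** A reader might take it as settled that the covariates enter the model. The documents do not support that. A dataset that includes covariates, or covariates used in designing an algorithm, need not mean input features, and sections e) and f) describe images as the input. Objective b) mentions the same variables as a description of a diverse validation set. This stands, and the point is therefore conditional. It does not remove the point: an image-only model would not be inflated directly, but its value beyond those items would still be unknown.

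**Benchmark models are often left to the SAP.** This is fair in general. Here, however, the Protocol itself names the comparison that ends the analysis and describes it in CNN terms. Training methodologies could be stretched to mean training with and without covariates. The text does not say so, and that would still supply no covariate-only model.

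**No objective claims superiority over a questionnaire.** This is correct: agreement with DEXA answers the accuracy objective as stated. But a conclusion about what X-ray images predict, and the use proposed in objective g), both rest on what the image contributes.

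**The trial can still find out.** A reader might infer that the study is unable to answer the question. That goes too far. The fields to be collected allow the comparison, and the planned correlations show in part how each covariate tracks BMD. The gap lies in the analysis as planned.

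**Conclusion.** The point holds in conditional form. The Protocol leaves open whether covariates are model inputs, and on either reading the one named model comparison cannot isolate the image's contribution. Under the assumed correlations, the image's own MAE gain lies between 0% and 22%, and the planned metrics would not locate it. That range rests on assumed PCCs and on the √(1 − r²) relation. No figure in the Protocol narrows it.

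Two stronger inferences should be avoided. Reading only the interior cells of the table would suggest that the image always adds about 8% to 18%; the corners of the same grid are 0% and 22%. And although a reader might count menopausal status among the risk factors that the Introduction reports, its figures and statements there concern sex, age, diabetes, cardiovascular disease and multimorbidity.

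This is a cheap improvement. The gap does not invalidate the study.

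**What to change.** In Methodology f) Statistical Analysis:

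1. State whether clinical covariates are inputs to the evaluated model, and bring the Rationale and sections d) and e) into line with that statement.
2. On the same folds, and in the same patients with the needed covariates recorded, fit a covariate-only regression, an image-only CNN and, if covariates are inputs, the combined model. The regression should use at least age, sex, BMI and menopausal status, plus diabetes and cardiovascular disease where available.
3. Report paired differences in MAE, PCC and AUPRC against the covariate-only model, with 95% intervals from a bootstrap over patients.
4. Base any claim about what the X-ray contributes on those differences.

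**Cost.** A few extra model fits and no new recruitment. Some retrospective patients may drop out of this comparison: the retrospective procedure names images and BMD reports from radiology, while menopause, diabetes, height and weight are on the interview questionnaire, so completeness of these items is not assured. The apparent benefit of the AI may also look smaller.

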• Introduction: Globally, osteoporosis poses a significant public health challenge, with an estimated 200 million patients affected worldwide and about it is responsible for nearly 9 million fractures annually, indicating its profound impact on morbidity, mortality, and healthcare costs [11]. In Bangladesh, the prevalence of osteoporosis is concerning, with a study revealing that among a cohort of 526 individuals, 37.3% are at risk of developing the condition [8]. The risk is notably higher in females (43.2%) compared to males (30.3%) and escalates with age, particularly after 50 years, reflecting global trends. Furthermore, the presence of diabetes and cardiovascular diseases significantly increases the risk, with a striking 78% of cardiovascular patients being at risk. Notably, individuals with multimorbidity present an even higher prevalence rate of 90%. This underlines an urgent need for effective screening and early detection strategies to mitigate the burden of osteoporosis, especially in resource-constrained settings.

Recent advancements in deep learning, particularly deep learning, have shown promise in utilizing plain radiographs for BMD prediction, potentially bypassing the need for more expensive and less accessible DEXA scans [12][13]. Studies leveraging CNNs have been successful in extracting clinically relevant features from X-ray images to predict BMD and assess fracture risk, demonstrating AI's potential in osteoporosis screening [14].

Despite these advancements, the application of AI in osteoporosis diagnosis faces challenges, notably the generalizability of models across diverse populations and healthcare settings. Most existing studies utilize datasets from localized patient populations and are often limited by the availability and quality of annotated data. This raises concerns about the models' performance and applicability in different regions, particularly in low- and middle-income countries where the disease burden is highest, and healthcare resources are scarce.

To address these gaps, our research aims to develop and evaluate an AI model for BMD prediction from X-ray images, with a particular focus on enhancing model generalizability and diagnostic accuracy. We intend to collect a comprehensive dataset comprising X-ray images, BMD measurements from local healthcare facilities. This diverse dataset will enable us to train and validate AI models that can robustly predict osteoporosis across different patient populations.

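### The covariate 'correlation analysis' is read as showing what influences bone health, but no adjustment for age or sex is stated, so an association for a comorbidity or menopause could reflect age or sex alone (minor)

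*Protocol*

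**What the plan says.** Three places in the protocol bear on this.

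- **Utilization of Results, c) Correlation Analysis.** The aim is to "explore and identify significant relationships between BMD or osteoporosis and collected clinical covariates such as age, gender, menopausal status, cardiovascular diseases, and diabetes". Age and gender stand in the list beside the comorbidities, not as adjustment variables. The purpose follows: "This analysis aims to enhance understanding of the factors influencing bone health, contributing to personalized and more precise osteoporosis risk assessment and management strategies".
- **Methodology, e) Data Interpretation.** Before model training, an exploratory look at the data covers how patients are distributed over demographic and clinical factors, "including age, gender, menopausal status, presence of cardiovascular diseases, diabetes, and their correlation with BMD values".
- **Methodology, f) Statistical Analysis.** Here "our statistical analysis will concentrate on evaluating the artificial intelligence model's capability to predict BMD from X-ray images accurately". The section gives performance metrics and k-fold cross-validation, and no method for covariate associations.

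On the background, the Introduction says that risk "escalates with age, particularly after 50 years, reflecting global trends", and gives 43.2% at risk among females against 30.3% among males. Methodology a) admits any gender and any age from 18. Methodology d) lists age, gender, BMI, menopausal status, diabetes and cardiovascular disease among the recorded fields.

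**The concern.** Item c) fixes three things: a label for the method (correlation), a criterion (significance) and an interpretation (influence on bone health, carried into risk assessment and management). The interpretation is stronger than the named method can bear. By the protocol's own account, age and sex are related to the outcome. Any covariate that is also related to age or sex will show a crude association with BMD even if it has no relation of its own. Menopausal status is the clearest case: it applies only to women and is tied to age, so in a mixed sample of adults from 18 it cannot be read apart from either.

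At stake is a secondary conclusion. The study could name a comorbidity as a bone-health factor, and carry it into personalised risk assessment, when the association is only that affected patients are older.

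**Working it through.** **The plan's own figures.** The covariate aim has no figure of its own. The only computed figures are the sample sizes, and they reproduce with z = 1.96:

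- N_sen = 1.96² × 0.911 × 0.089 / (0.05² × 0.373) = 334.01, rounded up to 335.
- N_spec = 1.96² × 0.689 × 0.311 / (0.05² × 0.627) = 525.13, rounded up to 526. The target is then set at 600.

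I use n = 600 below.

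**How small an association becomes significant.** The smallest |r| with two-sided p < 0.05 is t/√(n − 2 + t²). At n = 600 this is 1.964/√(598 + 3.857) = 0.080.

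**What age alone can produce.** If a covariate X is related to BMD only through age, then r(BMD, X) = r(BMD, age) × r(age, X). A product of 0.08 is enough to sit at the threshold, for example 0.4 × 0.2. The chance of significance follows from Fisher's z. For −0.3 × 0.3 = −0.09: atanh(0.09) × √597 = 2.205, and Φ(2.205 − 1.96) = 0.60. On the same formula:

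| r(BMD, age) | r(age, X) | Chance of p < 0.05 |
|---|---|---|
| −0.2 | 0.1 | 8% |
| −0.2 | 0.2 | 16% |
| −0.3 | 0.3 | 60% |
| −0.4 | 0.3 | 84% |
| −0.5 | 0.4 | over 99% |

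**The same in BMD units, for cardiovascular disease.** All inputs here are assumptions: true effect zero, 150 patients with disease and 450 without (25%), age mean 55 and SD 13, residual BMD SD 0.12 g/cm². The odds of disease rise 2% to 8% per year of age, and BMD falls by 0.001 to 0.005 g/cm² per year. The crude difference is the slope times the age gap between groups. Its standard error is SD × √(1/150 + 1/450), where the SD combines the residual with the within-group age spread.

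Worked case, 6% per year and −0.005: the gap is 8.9 years, so the difference is −0.0445. The within-group age SD is about 12.4, so the SD is √(0.12² + 0.005² × 12.4²) = 0.135 and the SE is 0.135 × 0.0943 = 0.0127. The ratio is about 3.5, and the chance of p < 0.05 is about 94%.

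| Rise in odds per year | Age gap (years) | Slope −0.001 | Slope −0.003 | Slope −0.005 |
|---|---|---|---|---|
| 2% | 3.3 | 6% | 13% | 25% |
| 4% | 6.3 | 9% | 36% | 70% |
| 6% | 8.9 | 12% | 62% | 94% |
| 8% | 11.1 | 16% | 80% | 99% |

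At slopes of −0.003 to −0.005 and odds rising 4% to 8%, the crude differences run from −0.019 to −0.055 g/cm².

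**With age in the model.** Simulating the same twelve cases (3,000 studies each) and adding age as a linear term, the rejection rate is 4.4% to 6.0%, which is the nominal 5% within simulation error. This holds because the simulated age effect is itself linear.

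**The case against.** The strongest reply is that the protocol never says the analysis will be unadjusted or done one covariate at a time. Item c) speaks only of relationships with a list of covariates, and a multivariable regression would satisfy that sentence. A statistical analysis plan, not shown here, may well specify one. This stands: a reader might infer that the protocol commits to pairwise crude tests, and the text does not support that. Silence on adjustment would not by itself be a point. What remains is what item c) does state: a correlation analysis, significance as the criterion, and influence as the conclusion. That conclusion is too strong as worded, whatever a later plan adds.

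A reader might also take the correlations in Data Interpretation as the flawed method. They are not. That section describes the data set before training and draws no inference, and crude correlations are acceptable there.

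The aim is also peripheral. Covariate association is not among specific objectives a) to g), where objective b) uses the covariates only to describe the validation population. Against this, Utilization of Results lists item c) among the algorithm's primary objectives and directs it to risk assessment and management. The Rationale does use age together with the other covariates, but as inputs to a prediction model, which does not adjust a separate association analysis.

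Finally, none of the inputs to the size of the problem comes from the documents. That cardiovascular disease and diabetes become commoner with age is general knowledge and is not stated in the protocol. With weak age slopes the excess nearly vanishes, and only cardiovascular disease was simulated.

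**Conclusion.** The point holds as a minor one. Item c) pairs a correlation analysis with a conclusion about influence, states no adjustment, and applies this to a sample in which age and sex vary widely and are related to the outcome by the protocol's own account. Followed as written, it could report an age- or sex-driven association as a bone-health factor. It is not shown that it would: the false-significance rate under no true effect runs from near the nominal 5% to 99%, and where the study falls in that range depends on age slopes the documents do not give. The range rests on 600 patients with complete covariates, 25% with cardiovascular disease and the assumed age and BMD distributions.

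A reader might infer that the AI model's evaluation is compromised. It is not: the performance metrics, the cross-validation and the sample size do not depend on this analysis.

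**What to change.** Change item c) of Utilization of Results only:

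- State that associations of BMD with diabetes and cardiovascular disease will come from a regression adjusted for age and sex, and for BMI where it is recorded.
- Assess menopausal status in women only, adjusted for age.
- Report coefficients with 95% confidence intervals and the number of patients with complete covariates.
- Replace the wording on influence with *factors associated with BMD among patients who had both X-ray and DEXA*.

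The descriptive correlations in Data Interpretation can stay.

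**Cost.** No new fields are needed, since Methodology d) already lists these variables. Fewer covariates will appear significant, and the estimate for menopausal status may be imprecise because it is closely tied to age. Retrospective records are drawn from X-ray images and BMD reports, while the comorbidity, height and weight items sit on an interview form. Some retrospective patients may therefore lack covariates and drop out of this analysis, which is why the complete-covariate count should be reported.
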